9.7.1.5 Safety Evaluations

Safety assessments were summarized for the Safety population. No formal hypothesis testing was performed.

9.7.1.5.1 Extent of Exposure

The number of days from first to last dose was summarized descriptively for each treatment group. Percent compliance for the entire study was calculated as follows:

$$\text{Number tablets missed} = (\text{number returned} - (2 \times \text{number of days off study}))$$

$$\text{Number tablets expected} = 2 \times \text{number of days on study}$$

$$\text{Percent Compliance} = (1 - (\text{number missed} / \text{number expected})) \times 100.$$

A subject was considered on-study from Visit 1 until study completion or premature discontinuation of study drug. Percent compliance was summarized descriptively for each treatment group.

9.7.1.5.2 Adverse Events

All AEs were classified by the MedDRA with respect to system organ class and preferred term. The number and proportion of subjects who experienced treatment-emergent adverse events (TEAEs), defined as events that began after receipt of randomized study drug, were summarized by treatment group for the following:

- By system organ class and preferred term
- By intensity (mild, moderate, or severe/life threatening/death), system organ class, and preferred term
- By relationship to study drug (not related or related), system organ class, and preferred term
- By weight tertile, system organ class, and preferred term
- By age tertile, system organ class, and preferred term
- SAEs by system organ class and preferred term
- SAEs by relationship to study drug (not related or related), system organ class, and preferred term
- SAEs by weight tertile, system organ class, and preferred term
- SAEs by age tertile, system organ class, and preferred term
- AEs resulting in discontinuation of study drug by system organ class and preferred term

The number and percent of subjects reporting at least 1 TEAE of hypotension (eg, blood pressure decreased, blood pressure diastolic decreased, blood pressure systolic decreased, hypotension, procedural hypotension), loss of consciousness, dizziness (eg, dizziness, dizziness exertional, procedural dizziness), presyncope, or syncope (syncope, syncope vasovagal) and the number and percent of subjects reporting each of the listed preferred

terms were summarized by treatment group. The 2 summaries were repeated by age tertiles and weight tertiles.

The number and percent of subjects reporting at least 1 TEAE of death, hospitalization for heart failure, or transplant and the number and percent of subjects reporting each of the listed preferred terms were summarized by treatment group. The 2 summaries were repeated by age tertiles and weight tertiles.

9.7.1.5.3 Clinical Laboratory Tests

Laboratory values were converted to the project-defined unit of measurement before analysis. Clinical laboratory variables were presented in 2 ways. First, change from baseline to Week 26 (study completion) was summarized descriptively for each treatment group. The baseline value was defined as the last assessment on or before dosing at Visit 1. Second, the number and proportion of subjects with treatment-emergent abnormal laboratory values were tabulated and the subjects identified. Treatment-emergent abnormal laboratory tests were those in which the baseline value was within the laboratory normal reference range and the postbaseline value was abnormal (ie, met Grade III or Grade IV toxicity criteria from the National Cancer Institute Common Terminology Criteria). All laboratory values obtained after Visit 1 were included in the analysis.

9.7.1.5.4 Vital Signs

Change from baseline (last vital sign value before the first dose of study drug at Visit 1) to each scheduled assessment was summarized descriptively by treatment group for each vital sign variable. Vital signs that were potentially clinically significant were identified according to prespecified criteria (listed in the SAP) and summarized descriptively by treatment group.

9.7.1.5.5 Prior and Concomitant Medications

The Concomitant Medications World Health Organization drug dictionary was used to classify all medications with respect to the Anatomical-Therapeutic-Chemical classification and preferred drug name. Prior and concomitant drug usage was summarized by Anatomical-Therapeutic-Chemical level 3 and preferred drug name. Medications with a start date before the first dose of study drug were considered prior medications. Medications with a stop date after the first dose of study drug or ongoing at study completion/discontinuation were considered concomitant medications. Therefore, medications that started before the study and continued into the study were counted as both prior and concomitant medications.

9.7.2 Determination of Sample Size

A sample size of 198 subjects per group would provide 90% power to detect a mean treatment group difference in change from baseline to Week 26 in maximal VO₂ scores of 10% (ie, an improvement of 2.8 mL/kg/min in the udenafil group compared to zero change in the control group, assuming a Type I error of 0.05 and standard deviation of 7.235). A difference of 2.8, equivalent to a 10% increase from a baseline of 28 mL/kg/min, represents approximately 0.4 standard deviations.

9.8 Changes in the Conduct of the Study or Planned Analyses

9.8.1 Changes in the Conduct of the Study

The original protocol, dated 09 March 2016, was amended 3 times. A copy of the final study protocol (Protocol PHN-Udenafil-02, dated 31 August 2017) is provided in [Appendix 16.1.1](#).

Version 2 of the protocol (04 May 2016) included the following substantive modifications to the original protocol:

- Added a DSMB review of all data after the first 50 subjects had completed the study.
- Added the opportunity for subjects to enroll in a heart rhythm-monitoring subset of the FUEL study.

Version 3 of the protocol (30 May 2017) included the following substantive modifications to Version 2 of the protocol:

- Conversion of Visits 2 and 3 to telephone calls, removing vital sign measurements.

Version 4 of the protocol (31 August 2017) included the following substantive modifications to Version 3 of the protocol:

- Addition of inclusion criterion #4, which required potential participants to be on anti-platelet or anticoagulant therapy.
- Addition of exclusion criterion #26, which excluded potential participants if they had a history of clinically significant thromboembolic event.

9.8.2 Changes to Planned Analyses

9.8.2.1 Changes Between Protocol Finalization and Final Statistical Analysis Plan

The SAP was finalized 23 June 2016. Key changes to statistical analyses between protocol finalization and the final SAP are described below.

The protocol defined 2 non-ITT analysis populations. The SAP replaced these non-ITT analysis populations by defining the more traditional Per Protocol population. In addition, the SAP provided a definition for the Safety population.

The protocol stated that potential differential impact of continuous age on treatment outcomes would be assessed and that a treatment by subpopulation interaction test would be conducted to identify differential treatment effects. Tests for treatment by subpopulation were not performed due to the low power of the tests.

The protocol also stated that treatment group differences would be assessed within subpopulations if the interaction p-value was <0.10 . These tests were not performed due to their potentially low power and bias due to lack of randomization within each subpopulation.

Minor clarifications were made to imputations for missing values.

Differences between the SAP and analyses presented in the clinical study report include:

- Presentation of the following for exercise capacity:
 - Percent predicted maximal VO_2
 - Heart rate at peak exercise
- Additional specific variables related to ventricular performance were summarized in the statistical tables.
- Friedman's test using ventricular morphology (single left versus single right or mixed) as the stratification factor was not used to assess treatment group differences for endpoints associated with the PedsQL and PCQLI. Differences were assessed using the same ANCOVA model as the other secondary endpoints.
- The qualitative estimate of atrioventricular valve insufficiency was not assessed.

- Subgroup analyses of AEs were also performed for gender, race, and ethnicity.
- Descriptive statistics of udenafil and metabolite concentrations were provided.

9.8.2.2 Changes Between Finalization of Statistical Analysis Plan and Blind Break

Key changes to statistical analyses between SAP finalization on 23 June 2016 and blind break on 19 July 2019 are described below.

Treatment group differences for the primary efficacy endpoint were summarized descriptively for subjects on afterload reducing agents in the study versus subjects who were not on afterload reducing agents in the study.

Analyses by visit were updated to account for protocol version 3, which replaced in-person Visits 2 and 3 (at Weeks 2 and 13, respectively) by telephone calls, and to remove collection of vital sign measurements at those time points.

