9.4.7 Prior and Concomitant Therapy

Subjects were to be treated with other medications at the discretion of their physicians. Management could have been symptomatic treatment (eg, hypotension from overdose or other cause) or observation and monitoring (eg, priapism). At study visits, current

medications were recorded on the study forms. If a subject began open-label use of any PDE-5 inhibitor at any time during the study, withdrawal from study drug was required. The following drug interactions have been observed with PDE-5 inhibitors including udenafil:

- Medications or other substances that strongly inhibit CYP3A4 including, but not limited to, erythromycin, indinavir, nelfinavir, clarithromycin, fluconazole, itraconazole, ketoconazole, posaconazole, voriconazole, and nefazodone.
- Medications or substances that strongly induce CYP3A4 including, but not limited to, carbamazepine, phenobarbital, phenytoin, rifabutin, rifampin, and St. John's Wort.
- Alpha blockers
- Intravenous inotropic drugs
- Bosentan
- Ritonavir
- Medications with a drug interaction that were to be avoided:
 - Boceprevir
 - PDE-5 inhibitors including sildenafil
 - Telaprevir
 - Vasodilator (organic nitrates) including isosorbide dinitrate, isosorbide mononitrate, and nitroglycerin
 - Soluble guanylate cyclase stimulators
- Select antihypertensives including amlodipine, angiotensin II receptor blockers, enalapril, and metoprolol were to be used with caution, as small decreases in blood pressure occurred when udenafil was co-administered with these agents.

Grapefruit juice was to be limited or avoided throughout study participation, as it may increase serum levels and/or the toxicity of udenafil. In preparation for EndoPAT testing, subjects were required to abstain from caffeine and to have fasted for 8 hours prior to testing.

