Table 10: Prior Medications Used by $\geq 5\%$ of Subjects in Either Treatment Group (Safety Population)

ATC Class (Level 3) ^a Preferred Drug Name	Udenafil (N=200) n (%)	Placebo (N=200) n (%)
≥ 1 non-study medication	195 (97.5)	198 (99.0)
ACE inhibitors, plain	107 (53.5)	107 (53.5)
Enalapril	55 (27.5)	62 (31.0)
Lisinopril	48 (24.0)	41 (20.5)
Antithrombotic agents	189 (94.5)	193 (96.5)
Acetylsalicylic acid	179 (89.5)	187 (93.5)
Warfarin	14 (7.0)	7 (3.5)
Beta blocking agents	16 (8.0)	18 (9.0)
Carvedilol	4 (2.0)	11 (5.5)
Beta-lactam antibacterials, penicillins	12 (6.0)	13 (6.5)
Amoxicillin	9 (4.5)	10 (5.0)
Cardiac glycosides	17 (8.5)	11 (5.5)
Digoxin	17 (8.5)	11 (5.5)
High-ceiling diuretics	18 (9.0)	14 (7.0)
Furosemide	18 (9.0)	13 (6.5)
Hypnotics and sedatives	10 (5.0)	5 (2.5)
Melatonin	10 (5.0)	5 (2.5)
Multivitamins, combinations	24 (12.0)	26 (13.0)
Multivitamins	21 (10.5)	24 (12.0)
Potassium-sparing agents	12 (6.0)	14 (7.0)
Spironolactone	12 (6.0)	14 (7.0)
Vitamin A and D, incl. combinations of the two	14 (7.0)	13 (6.5)
Colecalciferol	13 (6.5)	12 (6.0)

ACE=angiotensin-converting enzyme; ATC=Anatomical-Therapeutic-Chemical; incl=including

a Subjects prescribed 2 or more drugs within an ATC class are counted only once at the class level. Therefore, the sum of preferred drug name frequencies can exceed the class frequency.

Source: [Table 14.3.25](#)

Program: [T_14_3_25.sas](#)

All but 1 subject in each treatment group reported at least 1 concomitant medication.

Frequently reported concomitant medications ($\geq 20\%$ of subjects in either treatment group) included acetylsalicylic acid (92.5% udenafil, 96.0% placebo), enalapril (28.5% udenafil,

31.0% placebo), lisinopril (25.0% udenafil, 20.0% placebo), and paracetamol (20.5% udenafil, 14.0% placebo).

The use of concomitant medications was similar between treatment groups ([Table 11](#)). Concomitant medications are provided by subject in [Listing 16.2.8.4.1](#) and [Listing 16.2.8.4.2](#).

Table 11: Concomitant Medications Used by ≥5% of Subjects in Either Treatment Group (Safety Population)

ATC Class (Level 3) ^a Preferred Drug Name	Udenafil (N=200) n (%)	Placebo (N=200) n (%)
≥1 non-study medication	199 (99.5)	199 (99.5)
ACE inhibitors, plain	110 (55.0)	106 (53.0)
Enalapril	57 (28.5)	62 (31.0)
Lisinopril	50 (25.0)	40 (20.0)
Adrenergics for systemic use	16 (8.0)	12 (6.0)
Salbutamol	11 (5.5)	8 (4.0)
Angiotensin II antagonists, plain	11 (5.5)	5 (2.5)
Losartan	10 (5.0)	5 (2.5)

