The treatment group difference (udenafil minus placebo) for change in VO_2 at VAT (mL/min) from baseline to Week 26 was positive for all subgroups ([Figure 4](#)). Positive differences indicate greater mean improvement from baseline for udenafil than for placebo.

Treatment group differences are also presented in mL/min without imputation by gender (Table 14.2.3.1.2.1), race (Table 14.2.3.1.2.2), ethnicity (Table 14.2.3.1.2.3), ventricular morphology (Table 14.2.3.1.2.4), age at Fontan surgery (Table 14.2.3.1.2.5), baseline serum BNP (Table 14.2.3.1.2.6), percent of predicted maximal VO₂ at baseline (Table 14.2.3.1.2.7), and use of afterload reducing agents (Table 14.2.3.1.2.8).

Figure 4: Treatment Group Difference in Mean VO₂ (mL/min) at VAT With 95% Confidence Interval for Change Between Week 26 and Baseline Visits in Subpopulations Using Last Observation Carried Forward (ITT Population)

%p=percent predicted; BNP=brain natriuretic peptide; ITT=intent-to-treat; VAT=ventilatory anaerobic threshold;
VO₂=minute oxygen consumption; yrs=years

[figure not shown]
Note: No imputation was performed. Subjects with unknown race and ethnicity were excluded from the respective analysis.

Source: [Figure 14.2.2.1.6](#)

Program: [f_forestplot](#)

The treatment group difference (udenafil minus placebo) for change in VO₂ at VAT (mL/kg/min) from baseline to Week 26 was positive for all subgroups (Figure 5). Positive differences indicate less mean deterioration from baseline for udenafil than for placebo.

Figure 5: Treatment Group Difference in Mean VO₂ (mL/kg/min) at VAT With 95% Confidence Interval for Change Between Week 26 and Baseline Visits in Subpopulations Using Last Observation Carried Forward (ITT Population)

%p=percent predicted; BNP=brain natriuretic peptide; ITT=intent-to-treat; VAT=ventilatory anaerobic threshold;
VO₂=minute oxygen consumption; yrs=years

Note: No imputation was performed. Subjects with unknown race and ethnicity were excluded from the respective analysis.

Source: [Figure 14.2.2.1.7](#)

Program: [f_forestplot](#)

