11.4.5 Drug-Drug and Drug-Disease Interactions

Drug-drug and drug-disease interactions were not assessed.

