6.4.4 Subpopulation s

Treatment group differences for the primary efficacy endpoint will be summarized descriptively for the following subpopulations based on the following baseline characteristics:

- Gender (female, male)
- Race (Asian, African-American, Caucasian, other)
- Ethnicity (Hispanic, non-Hispanic)
- Ventricular morphology (single left, single right or mixed)
- Age at Fontan surgery (< 3 years, \geq 3 years)
- Baseline serum BNP level (< median, \geq median)
- Percent of predicted maximal VO_2 at baseline (< 75%, \geq 75%)

A 95% confidence interval of the difference in treatment group means will be provided within each subpopulation.

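### The added afterload-reducing-agent subgroup is defined by use during the study rather than at first dose, so randomisation does not protect the split, although the likely effect is small

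*Protocol*

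**What the plan says.** SAP 6.4.4 plans descriptive summaries of the primary endpoint "for the following subpopulations based on the following baseline characteristics". Afterload-reducing agents are not on its list.

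Protocol section 9.8.2.2 records an addition made after the SAP was final and before the blind was broken: a descriptive summary of the primary endpoint for "subjects on afterload reducing agents in the study versus subjects who were not on afterload reducing agents in the study". It does not say which drugs count or when use must have begun. Section 11.4.2.8 shows that the split was applied to maximal VO2 in both units and to VO2 at VAT in mL/min, the last under "use of afterload reducing agents (Table 14.2.3.1.2.8").

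Section 9.4.7 asks for caution with select antihypertensives because "small decreases in blood pressure occurred when udenafil was co-administered with these agents". It gives amlodipine, angiotensin II receptor blockers, enalapril and metoprolol as examples. Section 11.4.5 states: "Drug-drug and drug-disease interactions were not assessed".

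**The concern.** A subgroup fixed at baseline keeps the randomised comparison within each stratum. A subgroup fixed by what happens during the study does not, because a subject who starts an agent after the first dose moves into the user stratum. If starting or avoiding the drug depends on blood pressure, and blood pressure depends on the assigned arm, the udenafil-placebo difference within a stratum can be distorted. SAP section 8.0 itself declines within-subgroup tests, partly because of possible bias from the lack of randomisation within subpopulations. A split by in-study use is more exposed to that bias than the listed baseline splits.

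A second, lesser gap is on safety. Section 9.4.7 points to a possible blood-pressure effect of co-medication, but the split was used only for exercise endpoints. Tables 41 and 42 are by treatment group alone, and the Table 41 model has treatment as its only factor. Adverse-event subgroups are gender, race, ethnicity, age and weight. The dizziness/syncope cluster is split only by age and weight. The safety tables listed in section 14.3 include none by co-medication.

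**Working it through.** **1. Reproduce the plan's figures.** Table 11 gives concomitant ACE inhibitors as 110/200 = 55.0% on udenafil and 106/200 = 53.0% on placebo, pooled 216/400 = 54.0%. Table 10 gives prior use as 107/200 in each arm, pooled 214/400 = 53.5%. All match the printed percentages.

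**2. Does in-study use include new starts?** By section 9.7.1.5.5, prior means started before the first dose. Concomitant means stopped after the first dose or still ongoing. Let P be prior users, C concomitant users, S prior users who had stopped by the first dose, and N users who had none before it. Then C = P − S + N, so N = C − P + S.
- Udenafil: N = 110 − 107 + S = 3 + S, so at least 3.
- Placebo: N = 106 − 107 + S = S − 1, which may be zero.

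This treats the ACE-inhibitor class as a stand-in for the undefined list of agents, and Table 11's definition as the meaning of in-study use.

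**3. How far could three subjects move the result?** Assume that all 3 differ from the rest of their stratum in the same direction by one SD of change in maximal VO2 (238 mL/min, Table 13). The SE of the overall treatment difference is 22.709 mL/min (Table 13). In a stratum holding a share f of subjects it is roughly 22.709/√f.
- Users: 3 × 238/110 = 6.5 mL/min, against 22.709/√0.54 = 30.9. Ratio 0.21.
- Non-users, if the 3 return there (90 + 3 = 93): 3 × 238/93 = 7.7 mL/min, against 22.709/√0.46 = 33.5. Ratio 0.23.

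**4. How many subjects does section 9.4.7 concern?** From Table 11, enalapril 57 + 62 = 119/400 (29.8%) and angiotensin II antagonists 11 + 5 = 16/400 (4.0%). With no overlap that is at most 135/400 (33.8%). Amlodipine and metoprolol fall below the table's 5% display limit, so their counts are not shown. The 54% is the whole ACE-inhibitor class, including lisinopril (50 + 40 = 90), which section 9.4.7 does not name.

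**5. What would a blood-pressure split show?** Week 26 diastolic change in Table 41 is −3.01 (SD 9.644, n = 189) on udenafil and 0.05 (SD 10.696, n = 190) on placebo.
- Difference −3.01 − 0.05 = −3.06 mmHg.
- Pooled SD = √[(188 × 9.644² + 189 × 10.696²)/377] = 10.185.
- SE = 10.185 × √(1/189 + 1/190) = 1.046, giving p = 0.0037 (printed 0.004) and a 95% CI of about −5.1 to −1.0.

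Assume equal SDs and a user share f of 54% to 57%. ACE inhibitors and angiotensin II antagonists together lie between 216/400 = 54% and 232/400 = 58%.
- Half-width per stratum, 1.96 × 1.046/√f: 2.8 (users) and 3.0 (non-users) at 54%; 2.7 and 3.1 at 57%.
- Half-width of the contrast, 1.96 × 1.046 × √[1/f + 1/(1 − f)]: 4.1 mmHg.
- Difference between strata detectable with 80% power: (1.96 + 0.84) × 2.10 = 5.9 mmHg.
- With enalapril alone as the split (28.5% and 31.0%), the half-widths become 3.8 in users, 2.4 in non-users and 4.5 for the contrast.

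**The case against.** The strongest reply on the subgroup is that it hardly matters. The net shift is a handful of subjects, the summary is descriptive, it was added before unblinding, and no conclusion rests on it. Treatment was blinded. The suggested mechanism, avoiding antihypertensives on udenafil, would reduce use in that arm, whereas the net count rose. All of this stands, and it limits the point to a definition that should be corrected. It does not make in-study use a baseline characteristic. The higher angiotensin II antagonist count on udenafil (11 against 5) is not evidence of uneven reclassification, because no prior count is shown and a switch from an ACE inhibitor need not change stratum.

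On safety, a reader might infer that over half the trial was exposed to a flagged interaction, that udenafil lowered blood pressure generally, and that the report nonetheless declares those users safe. The documents do not support that reading:
- The named agents that can be counted reach at most about 34% of subjects, although the list in section 9.4.7 is open-ended.
- Only diastolic pressure differed, at Weeks 2 and 26. Systolic p-values were 0.682, 0.948 and 0.246.
- Section 12.6 limits its adverse-event subgroup statement to gender, race, ethnicity, age and weight, and its vital-sign statement concerns treatment groups. Section 11.4.5 discloses the gap.
- Table 37 has no hypotension or presyncope row, and its cluster total is 18 against 19. Table 42 shows low systolic values in 0 against 0 and low diastolic values in 4 against 4 subjects on Day 1.

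What remains to be split is mean blood-pressure change and dizziness or syncope. The contrast half-width of 4.1 mmHg exceeds the whole 3.06 mmHg effect, so the yield is modest.

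**Conclusion.** The point holds as a defect of definition. The afterload split rests on in-study use with no drug list or timing rule, and at least 3 udenafil subjects are ACE-inhibitor users only from the first dose onward. The stratum comparisons are therefore not fully randomised ones. The likely distortion is about 0.2 of a standard error if the net shift is close to the true one. Individual starts and stops are not visible in the tables, so the gross shift could be larger. The documents do not show that the subgroup results are materially biased, and the primary analysis is not affected.

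The missing safety split by co-medication is real but secondary. It would be an exploratory estimate, with precision that depends on the assumed user share and equal SDs. The section 12.6 subgroup statement needs no correction.

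**What to change.** 1. State which drugs count as afterload-reducing agents. Classify a subject as a user if an agent was started before the first dose and was ongoing at that dose. Rerun Tables 14.2.1.1.2.8, 14.2.2.1.2.8 and 14.2.3.1.2.8 on that flag, and say that it replaces the in-study definition.
2. Optionally, form a second first-dose flag for the agents named in section 9.4.7. Within users and non-users, tabulate by arm the change in systolic and diastolic pressure at each visit with data, and the dizziness/syncope cluster. Give 95% confidence intervals, including one for the contrast between strata, and label the tables exploratory and not powered. Weeks 2 and 13 have only 131 to 155 subjects per arm, so intervals there will be wider.

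The cost is two flags from medication dates already recorded, three reruns and a few descriptive tables. No new data are needed. The price is modest precision, lowest where the user group is small.
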